#### 10.3 Drug Interactions:

Strong CYP3A4 inhibitors such as ketoconazole may **increase** sunitinib or temsirolimus plasma concentrations. Selection of an alternate concomitant medication with no or minimal enzyme inhibition potential is recommended. Concurrent administration of these agents with the strong CYP3A4 inhibitor, ketoconazole, can result in increased drug levels. Co-administration of these agents with strong inhibitors of the CYP3A4 family (e.g., ketoconazole, itraconazole, clarithromycin, atazanavir, indinavir, nefazodone, nefazodone, nelfinavir, ritonavir, saquinavir, telithromycin, voriconazole) may increase drug concentrations. Grapefruit may also increase plasma concentrations of these agents.

A dose reduction for sunitinib should be considered when it must be co-administered with strong CYP3A4 inhibitors. Refer to the package insert for guidelines.

CYP3A4 inducers such as rifampin may **decrease** sunitinib and temsirolimus plasma concentrations. Selection of an alternate concomitant medication with no or minimal enzyme induction potential is recommended. Concurrent administration of these agents with the strong CYP3A4 inducer may reduce blood concentrations. Co-administration of these agents with CYP3A4 family (e.g., dexamethasone, phenytoin, carbamazepine, rifampin, rifabutin, rifapentine, phenobarbital, St. John's Wort) may decrease their concentrations. St. John's Wort may decrease sunitinib plasma concentrations unpredictably. A dose increase may be considered when it must be co-administered with CYP3A4 inducers. See package insert.

Temsirolimus is also an immune suppressor and care should be taken if patients require other immunosuppressive medication during therapy such as steroids.

## 11.0 Evaluation and Management of Toxicity

Patients will be seen every six weeks at the beginning of each cycle to assess toxicity and dose. Temsirolimus is standard of therapy used throughout the United States and the world. During temsirolimus therapy, patients may be treated off site at their local oncologist's office with the approval of the PI and following notification and approval by Dartmouth's local Institutional Review Board (IRB), the Committee for the Protection of Human Subjects (CPHS). All toxicity will be managed by Dartmouth's protocol physicians and nurses for those being treated through DHMC. For those patients treated through the UVM program, the UVM research staff will manage all toxicities and report them according to the protocol. We will describe the toxicity profile of the investigational regimen by tabulating the observed toxicity according to type and grade. We will compute the rates of serious grade 3 or worse toxicity (as defined using the NCI Common Toxicity Criteria Version 4.0). Toxicity will be carefully monitored during the course of the study, but there will be no formal stopping rules. At the investigator discretion, safety labs may be drawn as standard care to assess for toxicity outside of general visit timelines. However, if the rate of grade 3 or worse non-hematological toxicity exceeds 33% at any time, accrual will be suspended and the toxicity information will be reviewed by the investigators and the Norris Cotton Cancer Center's (NCCC) Safety and Data Monitoring Committee.

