## 8.1: Registration:

Patient registration will be done through [name] at NCCC:

[name]  
Hematology/Oncology  
Dartmouth Hitchcock Medical Center  
[name]  
[name]  
[contact]  
[contact]  
([contact])

Registration will include review of eligibility with source documentation. Eligibility will be assessed by a research nurse and the PI of the respective institutions with [name] or her designee at NCCC. PI signature on eligibility form will be delivered via Fax or mail to [name]. Each patient will be assigned a unique registration number and entered into the Velos Data Base in accordance with standard operating procedure.

Treatment calendars will be generated at NCCC and be made available to treating teams at the respective institutions. CRF will be completed on site and be sent to [name].

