### 11.1 Dose Modification and Monitoring of Toxicity

We will compute the rates of any toxicity and any grade 3 or worse toxicity (as defined using the NCI Common Toxicity Criteria Version 4.0). Toxicity will be carefully monitored during the course of the study, but there will be no formal stopping rules based on toxicity, as the alternating sequence of therapy uses the FDA approved doses for each therapy. Temsirolimus at the FDA approved dose has already been noted to be safe following sunitinib failure. However, if the rate of grade 3 or worse non-hematological toxicity exceeds 33% at any time, accrual will be suspended and the toxicity information will be reviewed by the investigators and the NCCC's Safety and Data Monitoring Committee.

**Sunitinib:** (adopted from Kollmannsberger C et al., Sunitinib therapy for metastatic renal cell carcinoma: recommendations for management of side effects. Can Urol Assoc J. 2007 June; 1 (2Suppl): S41-54):

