#### **Types of Report (see table):**

**Telephone report:** For grades 4 and 5 unexpected toxicity, a telephone or electronic mail and written report will go to the following groups: Dartmouth Medical School's Committee for the Protection of

Human Subjects (CPHS), UVM IRB, and the Norris Cotton Cancer Center's Data Monitoring and Safety Committee (DMSC). The telephone or electronic mail report will be within 24 hours from when the PI is notified of the toxicity. A written report will follow within 10 working days.

If the grade 4/5 unexpected toxicity is noted at a patient being treated at UVM, they will notify the contacts at NCCC by telephone or e-mail within 24 hours. (Contacts: [name] at [[contact]](mailto:[contact]) , [contact]) or [name] ([[contact]](mailto:[contact]), [contact])

**Written report:** An NCI adverse drug reaction form and copies of all available and updated study data will be provided within 10 working days to the CPHS and the DMSC. All toxicity will be reported using the NIH common toxicity form.

For grades 2 and 3 unknown toxicity, a written report will be sent within 10 working days to the DMSC and the CPHS. Grades 3 or worse known toxicity will be submitted as part of the study summary.

*Unknown Reaction*

Grades 2-3

Written report to CPHS and DMSC  
within 10 working days

Grades 4 and 5

Report by phone (e-mail) to CPHS and DMSC  
within 24 hours.  
Written report to follow within 10 working days.

*Known Reaction*

Grades 1-3

Not to be reported as ADRs.  
A report will be submitted as part of  
study summary to include only  $\geq$  grade 3.

Grades 4 and 5

Written report or e-mail to CPHS and DMSC  
within 10 working days

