## **18.0 STUDY CONDUCT/ETHICAL CONSIDERATIONS**

The possibility of adverse events to the subjects treated in this trial is real. The possibility of benefit is also real. In compliance with Federal Regulations, as well as proper ethical conduct, the patient is required to sign a consent form once he or she is satisfied that they understand all potential outcomes, both adverse and beneficial.

A patient is free to withdraw at any time during the study. No changes will be made to the study without approval by the IRB. All changes or observations during the trial that may increase the risk will be reported to the IRB and FDA.

The Norris Cotton Cancer Center's Safety and Data Monitoring Committee (SDMC) will monitor the study progress on a quarterly basis according to our Cancer Center's guidelines. Serious or unexpected adverse events will be reported immediately by the PI to the SDMC, Dartmouth Medical School's IRB, UVMs IRB and the FDA in accordance with NIH guidelines. These activities will ensure careful oversight of patient safety.

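### Can the 33% toxicity trigger stay silent because known, non-serious grade 3 reactions have no timed report?

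*Combined protocol and SAP*

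**What the plan says.** **Trigger.** Sections 11.0 and 11.1 use the same sentence: "if the rate of grade 3 or worse non-hematological toxicity exceeds 33% at any time, accrual will be suspended". Review by the investigators and the cancer center's monitoring committee follows. Both sections say there are no formal stopping rules, and 11.1 explains this by the use of approved doses.

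**Rates to be tabulated.** Section 11.0: "We will compute the rates of serious grade 3 or worse toxicity". Section 11.1: "We will compute the rates of any toxicity and any grade 3 or worse toxicity".

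**Reports (Section 15).** The text says of expected reactions: "Grades 3 or worse known toxicity will be submitted as part of the study summary". The table says of known grades 1-3: "Not to be reported as ADRs". It sends known grades 4-5 and unknown grades 2-3 to the ethics committee and the monitoring committee within 10 working days, and unknown grades 4-5 within 24 hours. For the second site: "If the grade 4/5 unexpected toxicity is noted at a patient being treated at UVM, they will notify the contacts at NCCC", also within 24 hours.

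**Other routes.**
- Section 18: "Serious or unexpected adverse events will be reported immediately by the PI to the SDMC", and the committee monitors the study quarterly.
- Section 7.3: adverse events are reviewed on Days 1 and 43 of each 84-day cycle.
- Section 8.1: "CRF will be completed on site and be sent to" a recipient whose name is removed from the public text, in a section on central registration.
- Section 19: community facilities are asked for weekly records, and toxicity management for their patients stays at the lead site.
- Section 11.0: second-site staff manage all toxicities and report them as the protocol requires.

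**The concern.** A rule that can act at any moment needs a running count. Section 5 names hypertension, fatigue and diarrhea as the main barrier to long-term sunitinib use. Grade 3 cases of these are non-hematological and expected, so the rule must count them, yet Section 15 gives them no deadline. The only route written specifically for the second site concerns unexpected grade 4/5 toxicity. Section 11.0 speaks of serious grade 3 or worse events where 11.1 speaks of any, and neither gives a unit or a denominator.

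If the count were built only from timed reports, or only from serious events, enrollment could continue above the sponsor's own limit without the promised review. That would be a matter of participant safety during accrual. The efficacy analysis would not be touched.

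**Working it through.** **1. What the rule needs.** The protocol gives no operating characteristics for the 33% rule, so there is no stated figure to reproduce. The largest denominator is the planned 37 patients (Section 17). Accrual over 36 months gives 37/12 = 3.1 patients per quarter. The first counts above 0.33 are 1 of 3, 2 of 4, 4 of 10, 7 of 20 and 13 of 37 (12/37 = 32.4%, 13/37 = 35.1%).

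**2. Complete counts, outcomes known at once.** The exact binomial probability that x/n exceeds 0.33 at one or more looks up to n = 37 is:

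| True rate | After every patient | At quarterly looks |
|---|---|---|
| 20% | 0.598 | 0.597 |
| 33% | 0.902 | 0.899 |
| 40% | 0.973 | 0.971 |
| 50% | 0.998 | 0.998 |

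On complete data the rule is sensitive, and checking only quarterly costs almost nothing.

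**3. Complete counts, delayed onset.** The simulation used 20,000 trials per setting, with 37 entries spread at random over 36 months. First-event onset was uniform over 12 weeks or 6 months (assumed), 33% was read as 0.33 or one third, and the denominator was all treated patients. Ranges run over these four settings.

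| True rate | Continuous count | Quarterly count |
|---|---|---|
| 40% | 87-95% | 80-91% |
| 50% | 98-99.6% | 97-99% |

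Mean patients entered at suspension, true rate 50%:
- Continuous: 4.5, 7.1, 5.5, 8.5.
- Quarterly: 6.9, 10.1, 8.3, 11.7.
- Differences: 2.4, 3.0, 2.8, 3.2, which is about one quarter's accrual.

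**4. Incomplete counts.** If a share u of affected patients is never counted, the rule sees the true rate times (1 - u).
- True 40%, u = 0.5: visible 0.40 × 0.5 = 20%; suspension 24-48%. A true 20% with full counts also gives 24-48%.
- True 40%, u = 0.75: visible 10%; suspension 7-20%.
- True 50%, u = 0.5: visible 25%; suspension 39-63%.

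The fall is exactly the assumed u and nothing else. The documents give no value for u, so the question is whether they imply one.

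**5. Do they imply one?**
- The trigger names all grade 3 or worse non-hematological toxicity. It does not refer to Section 15 and does not contain the word serious. The serious/any difference lies in separate sentences on descriptive rates, which are not limited to non-hematological events.
- Section 15 governs adverse-reaction reports to oversight bodies. It does not govern what the investigators may count.
- The table exempts no site. Known grade 4-5 and unknown grade 2-3 reactions at the second site also go to the lead center's committee within 10 working days. The 24-hour notice is an addition to this.
- A 10-day report of a known grade 4-5 reaction and its later listing in the study summary are compatible.
- Several dose-modification rules in Section 11.1 depend on grade 3, so staff must grade these events as they treat.

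**6. Unit and denominator.** At a true 20%, suspension is 24-48% for patients over all treated. It is 49-69% if only patients with an event or a completed 12-week cycle are in the denominator. It is 47-64% or 65-77% if events are counted, at an assumed average of 1.5 or 2 per affected patient. Every alternative examined makes the rule act more often, so this ambiguity does not silence it.

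**The case for a change.** The strongest case is that holding data is not the same as counting them. Days 1 and 43 collect adverse events but forward nothing. Case report forms travel with no deadline. The quarterly review covers study progress, and no sentence says it receives a cumulative grade 3 table. Nobody is named to compute the rate. With no other numeric safeguard, one reporting line would be cheap, and a needless pause leads only to review.

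Part of this stands. A known, non-serious grade 3 reaction has no timed report, and no owner, interval or denominator is stated. It does not stand that the trigger is therefore likely to be silent. That would require investigators charged with careful monitoring and with applying this limit to disregard events they had graded. It would also require the committee to review the trial four times a year without seeing its main toxicity. The serious/any mismatch is loose drafting about descriptive tables.

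Requiring two affected patients before the rule acts would answer a different worry, false alarms. At a true 20% it lowers suspension from 24-48% to 19-36%. At a true 50% it moves the pause from 4.5-8.5 patients to 6.3-9.7. That is a trade-off within the sponsor's rule, and it does not repair a gap.

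**Conclusion.** No change is called for. The protocol leaves bookkeeping detail unstated, and a team applying the trigger as written would supply it: patients with at least one grade 3 or worse non-hematological toxicity, serious or not, over all treated patients at both sites. If the count were refreshed only at quarterly reviews, the cost is 4 to 7 percentage points in the chance of suspension at a true 40%, 2 points or less at 50%, and about 2.4 to 3.2 more patients entered at 50%.

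This rests on three assumptions: the quarterly review sees a complete cumulative count; first events occur within 12 weeks to 6 months; and the differently ordered committee names in Sections 11, 15 and 18 refer to one body. The first matters most. If half of the affected patients really went uncounted, suspension at a true 40% would fall to 24-48%, but the documents give no ground for such a share.

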### 11.1 Dose Modification and Monitoring of Toxicity

We will compute the rates of any toxicity and any grade 3 or worse toxicity (as defined using the NCI Common Toxicity Criteria Version 4.0). Toxicity will be carefully monitored during the course of the study, but there will be no formal stopping rules based on toxicity, as the alternating sequence of therapy uses the FDA approved doses for each therapy. Temsirolimus at the FDA approved dose has already been noted to be safe following sunitinib failure. However, if the rate of grade 3 or worse non-hematological toxicity exceeds 33% at any time, accrual will be suspended and the toxicity information will be reviewed by the investigators and the NCCC's Safety and Data Monitoring Committee.

**Sunitinib:** (adopted from Kollmannsberger C et al., Sunitinib therapy for metastatic renal cell carcinoma: recommendations for management of side effects. Can Urol Assoc J. 2007 June; 1 (2Suppl): S41-54):

#### Dose modifications:

We will use the standard dose modification in 12.5 mg increments:

- Dose level 1: 50.0 mg for 4 weeks, 2 weeks off
- Dose level 2: 37.5 mg for 4 weeks, 2 weeks off
- Dose level 3: 25.0 mg for 4 weeks, 2 weeks off

Recovery to acceptable levels of toxicity should occur within 4 weeks before sunitinib or temsirolimus therapy can be continued.

Re-escalation to the previous dose level is suggested in the absence of grade 3 or higher hematologic treatment-related toxicity, or in the absence of grade 2 or higher non-hematologic treatment-related toxicity in the previous cycle.

Overall, clinical judgment based on the medical history and clinical status of individual patients should dictate the appropriate monitoring and actions, if any, to be taken in response to side effects.

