### **Gastrointestinal Toxicity:**

For grade 3 or 4 diarrhea treatment should be interrupted until diarrhea is grade 1 or less, or has returned to baseline. The sunitinib dose should be reduced by 1 dose level (12.5mg) in subsequent cycles.

Common antiemetics can be used to relieve nausea and vomiting. However, particular care should be used when sunitinib is combined with antidopaminergic agents such as domperidone, or 5HT3 antagonists, such as granisetron, ondansetron, and dolasetron, because they have been associated with QT/QTc interval prolongation or torsade de pointes.

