### **Hematologic**

Sunitinib induces neutropenia and thrombocytopenia in about 20% of patients. For grade 3 or 4 neutropenia or thrombocytopenia, or if thrombocytopenia persists for at least 5 days, the dose of sunitinib should be reduced in the next scheduled cycle.

Erythropoietic agents such as epoetin- $\alpha$  or darbepoetin- $\alpha$ , or blood transfusions may be used at the discretion of the treating physician to treat anemia.

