### **Skin**

Hand-foot syndrome presents as painful symmetric erythematous and edematous areas on the palms and soles, commonly preceded or accompanied by paresthesias, tingling or numbness. For  $\geq$  grade 3, sunitinib should be discontinued and after resolution to  $\leq$  grade 1, dose reduce to the next lowest dose tier.

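### The sunitinib re-escalation rule joins its two conditions with 'or', so it suggests a higher dose after toxicities for which the same section directs a reduction

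*Combined protocol and SAP*

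**What the plan says.** Section 11.1 (sunitinib, Dose modifications) lists three dose levels: 50, 37.5 and 25 mg daily for 4 weeks, each followed by 2 weeks off. On going back up a level, the rule reads: "suggested in the absence of grade 3 or higher hematologic treatment-related toxicity, or in the absence of grade 2 or higher non-hematologic". Both classes refer to treatment-related events, judged on the cycle just completed. The next sentence adds that "clinical judgment based on the medical history and clinical status of individual patients should dictate the appropriate monitoring and actions" to be taken.

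The toxicity-specific parts of the same section then say:

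- **Gastrointestinal:** "For grade 3 or 4 diarrhea treatment should be interrupted until diarrhea is grade 1 or less" or back to baseline, and "The sunitinib dose should be reduced by 1 dose level (12.5mg) in subsequent cycles".
- **Hematologic:** the first trigger is a neutrophil or platelet toxicity of grade 3 or 4, and the sentence goes on: "or if thrombocytopenia persists for at least 5 days, the dose of sunitinib should be reduced in the next scheduled cycle".
- **Skin:** for hand-foot syndrome of grade 3 or worse, stop sunitinib and, once it has resolved to at most "grade 1, dose reduce to the next lowest dose tier".

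Nothing in the protocol says that both re-escalation conditions must hold, or that the toxicity-specific rules take precedence over the re-escalation rule.

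**The concern.** The rule repeats its opening phrase on both sides of *or*. A single phrase covering both classes could have been read as *neither*. The repetition makes two separate conditions, and either one is enough. A patient with severe non-hematologic toxicity then qualifies through normal counts, and a patient with severe cytopenia qualifies through the lack of non-hematologic toxicity.

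What is at stake is dosing safety and consistency between treating teams. Section 11.0 has Dartmouth staff manage toxicity for their own patients, and for patients in the Vermont program "the UVM research staff will manage all toxicities and report them according to the protocol". Two teams therefore read this rule. Section 3.0 sets no fixed number of cycles, so the rule can be applied repeatedly in one patient.

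The concern is limited to four events: grade 3-4 diarrhea, grade 3 or worse hand-foot syndrome, grade 3-4 neutropenia and grade 3-4 thrombocytopenia. It does not extend to grade 3 fatigue, hypertension, hemorrhage or anemia, for which Section 11.1 directs no dose-level reduction. Nor does it extend to raised amylase or lipase, where resuming one tier lower is only permitted.

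**Working it through.** The plan gives no figure to reproduce here. The check is one of logic, plus simple dose arithmetic.

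**Inputs (all from Section 11.1, sunitinib).** Let *h* be the worst treatment-related hematologic grade in the previous cycle and *n* the worst non-hematologic grade.

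- Rule as written: re-escalate if *h* < 3 **or** *n* < 2.
- Rule with *and*: re-escalate if *h* < 3 **and** *n* < 2.

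**Step 1. Each event alone, in a patient already below 50 mg.**

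| Event in the previous cycle | (*h*, *n*) | Specific rule | With *or* | With *and* |
|---|---|---|---|---|
| Diarrhea, grade 3 | (0, 3) | reduce | re-escalate | no |
| Diarrhea, grade 4 | (0, 4) | reduce | re-escalate | no |
| Hand-foot syndrome, grade 3 | (0, 3) | reduce | re-escalate | no |
| Neutropenia or thrombocytopenia, grade 3 | (3, 0) | reduce | re-escalate | no |
| Neutropenia or thrombocytopenia, grade 4 | (4, 0) | reduce | re-escalate | no |
| Thrombocytopenia, grade 2, lasting at least 5 days | (2, 0) | reduce | re-escalate | re-escalate |

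The four named events contradict the specific rules under *or* and agree with them under *and*. The last row conflicts under both words, so changing the conjunction does not close that case.

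**Step 2. How far the conjunction matters.** Take grades 0 to 4 for each class, which gives 5 × 5 = 25 combinations.

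- With *or*, the rule blocks re-escalation only when *h* is 3 or 4 and *n* is 2, 3 or 4: 2 × 3 = 6 combinations. It suggests re-escalation in 25 − 6 = 19.
- With *and*, it suggests re-escalation only when *h* is 0, 1 or 2 and *n* is 0 or 1: 3 × 2 = 6 combinations.

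This grid describes the rule. It does not show how often patients fall in each cell.

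**Step 3. Size in dose.** Take a patient at 37.5 mg with grade 3 diarrhea and normal counts.

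- Current dose: 28 × 37.5 = 1,050 mg over the 28 dosing days.
- Re-escalation rule: 50 mg, 28 × 50 = 1,400 mg, a change of (50 − 37.5)/37.5 = +33%.
- Gastrointestinal rule: 25 mg, 28 × 25 = 700 mg, a change of (25 − 37.5)/37.5 = −33%.
- Ratio of the two instructions: 50/25 = 2, that is, two dose levels apart.

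This comparison can be made only at 37.5 mg. A patient at 50 mg has no higher level, and no level below 25 mg is listed.

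**The case against.** The strongest reply is that the two thresholds belong to two toxicity classes and that *or* means whichever class applies. If each event just seen is tested against its own class's threshold, grade 3 diarrhea or hand-foot syndrome fails the grade 2 test, grade 3-4 cytopenia fails the grade 3 test, and the four conflicts vanish. The text does not say this, however. If the class is instead the one that caused the earlier reduction, a conflict remains: a patient reduced for neutropenia who then has grade 3 diarrhea with normal counts still passes the hematologic test.

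A second reply is that a specific directive ordinarily outranks a general suggestion, and that the clinical-judgment sentence lets the physician follow the specific rule. This lowers the chance of harm considerably and is why the point is minor. But no precedence is stated, and the judgment sentence does not say how the two conditions combine.

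A third reply is that *and* may be stricter than the authors intended. A patient reduced for neutropenia whose counts have recovered would be held at the lower dose by an unrelated grade 2 non-hematologic event, such as fatigue, for which dose changes up to grade 3 are left to the treating provider. That cost is real. The sunitinib rules are adopted from a published recommendation that is not part of these documents, so intent cannot be settled from the text.

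**Conclusion.** The concern holds. Read as written, the re-escalation rule suggests a higher sunitinib dose after four toxicities for which the same section directs a lower one. For a patient at 37.5 mg the two instructions differ two-fold (50 against 25 mg).

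The conclusion rests on the literal reading of the rule, on each event occurring without a disqualifying toxicity in the other class, and on the patient being below 50 mg already. The documents give no rate from which to estimate how many patients this would affect. Severity is minor: the rule is a suggestion, judgment may override it, and *and* was probably intended. The sample size and primary analysis are unaffected.

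**What to change.** In Section 11.1 (sunitinib, Dose modifications), replace *or* with *and*, so that re-escalation needs a previous cycle free of both grade 3 or higher hematologic and grade 2 or higher non-hematologic treatment-related toxicity. Add a further condition: no event in that cycle that required a dose reduction. This covers thrombocytopenia below grade 3 that lasts at least 5 days. Leave the clinical-judgment sentence as it is, so that a physician can still depart from the rule when an unrelated grade 2 event is the only obstacle.

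The cost is one short wording amendment, which needs approval because Section 18.0 states that "No changes will be made to the study without approval by the IRB", and somewhat fewer re-escalations. No visits, patients or data fields are added.
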